8.1. Efficacy Assessments

8.1.1. Protocol-required Assessments

8.1.1.1. PMS Assessment

The 12-point Mayo score is an instrument designed to measure UC disease activity based on a combination of endoscopic findings and the patient's clinical characteristics.⁴⁰ The non-invasive PMS excludes the endoscopic component of the full Mayo scoring system and ranges from 0 to 9 points. The PMS consists of the following 3 subscores, each graded from 0 to 3, with higher scores indicating more severe disease:

- Stool frequency (0-3);
- Rectal bleeding (0-3);
- Physician global assessment (0-3).

Stool frequency subscore assessment:

- 0 = Normal number of stools;
- 1 = 1–2 stools more than normal;
- 2 = 3–4 stools more than normal;
- 3 = 5 or more stools than normal.

Rectal bleeding subscore assessment:

- 0 = No blood seen;
- 1 = Blood streaks seen in stool less than half the time;
- 2 = Blood seen in stool most of the time;
- 3 = Blood alone passes.

Physician global assessment subscore assessment:

- 0= Normal;
- 1= Mild Colitis;
- 2= Moderate Colitis;
- 3= Severe Colitis.

Each patient serves as his or her own control to establish the degree of abnormality of the stool frequency. The daily rectal bleeding score represents the most severe bleeding of the day. The physician global assessment subscore acknowledges the 2 other subscores (stool frequency and rectal bleeding), patient's recollection of abdominal discomfort, general sense of wellbeing, and other observations, such as physical findings and patient's performance status.

It is recommended that the same physician performs all such assessments for a particular study participant throughout the study.

PMS will be assessed at the baseline, Week 8 and Week 16 visits. Failure to assess PMS at these study visits will constitute a protocol deviation.

Endpoints based on the Partial Mayo scores are defined as follows:

- Clinical remission: total PMS of ≤ 2 with no subscore exceeding 1 point;¹²

- Clinical response: meeting one of the following criteria: (1) reduction in PMS of ≥ 2 points from baseline or (2) achieving clinical remission as described above.¹²

The FMS will be calculated if endoscopy is performed as SOC. The Mayo Endoscopic subscore assessed as SOC and PMS assessed as protocol-required assessment will be used to calculate FMS. Endoscopy is not a protocol-required procedure, nor a mandatory assessment for inclusion in the study.

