9.5.2. Primary Analysis

Proportions of participants achieving clinical, IBDQ and biochemical response* and remission† at Week 8 and Week 16 will be calculated and reported with the associated 95% Wilson confidence interval.

The course of continuous secondary outcomes (PROs and fCAL) over time will be depicted by box plots showing medians, quartiles, and outlying values.

* Clinical response: (1) Reduction in PMS from baseline of >2 points or (2) achieving clinical remission.¹²

IBDQ response: IBDQ score ≥ 16 points higher than IBDQ baseline score.

† Clinical remission: PMS of ≤ 2 with no subscore > 1 .¹²

IBDQ remission: IBDQ score ≥ 170 .¹²

Biochemical remission: fCAL concentration ≤ 250 mg/g.¹¹

Correlation between PMS, PROs, IBDQ score and fCAL concentrations will be assessed by the Spearman correlation coefficient.

The course of fCAL over time will be shown separately for participants with and without clinical response, as well as for participants with and without remission at Week 8 and Week 16.

These analyses will also be conducted on the subset of participants that complete 8 weeks of tofacitinib therapy.

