7.1 Outcome definitions

Table 7-a: Derivation of study outcomes

Outcome	Definition	eCRF sheet	Variable	Variable type	Derivation	Outcome type
PRIMARY OUTCOME						
Clinical response at W8	(1) reduction in PMS from baseline of ≥ 2 points or (2) achieving clinical remission	PMS	PMS score (see section 4.3) pms_stool_freq pms_rect_bleed pms_glob_ass	continuous	Yes: If (PMS at W8- PMS at baseline ≥ 2) OR PMS at W8 ≤ 2 AND pms_stool_freq<2 AND pms_rect_bleed<2 AND pms_glob_ass<2 at W8.	Binary: Yes, no
SECONDARY OUTCOMES						
Clinical response at W16	(1) reduction in PMS from baseline of ≥ 2 points or (2) achieving clinical remission		PMS score (see section 4.3) pms_stool_freq pms_rect_bleed pms_glob_ass	continuous	Yes: If (PMS at W16- PMS at baseline ≥ 2) OR PMS at W16 ≤ 2 AND pms_stool_freq<2 AND pms_rect_bleed<2 AND pms_glob_ass<2 at W16.	Binary: Yes, no
Clinical remission W8/W16	Clinical remission: PMS of ≤ 2 with no subscore >1		PMS score (see section 4.3) pms_stool_freq pms_rect_bleed pms_glob_ass	continuous	Yes: PMS at W8 (or 16) ≤ 2 AND pms_stool_freq<2 AND pms_rect_bleed<2 AND pms_glob_ass<2 at W8 (or 16).	Binary: Yes, no
CTU Bern	SAP for: Study A3921395 KIC-START		Version: 1.0			

CTU Bern	Template: Statistical Analysis Plan (SAP)	Version: 03
	Code: CS_STA_TEM-11	Valid from: 28.02.2019

u^b^b
UNIVERSITÄT
BERN

Outcome	Definition	eCRF sheet	Variable	Variable type	Derivation	Outcome type
IBDQ remission at W8/W16	IBDQ remission: IBDQ score ≥ 170		IBDQ score calculated as described in section 4.3 at W8 and 16	continuous	Yes: IBDQ at W8 (or 16) ≥ 170	Binary: Yes, no
IBDQ response at W8/W16	IBDQ response: IBDQ score ≥ 16 points higher than IBDQ baseline score		IBDQ score calculated as described in section 4.3 at baseline, W8 and 16	continuous	Yes: IBDQ at W8 (or 16) – IBDQ at BL ≥ 16	Binary: Yes, no
Biochemical remission at W8/W16	Biochemical remission: fCAL concentration $\leq 250 \mu\text{g/g}$		fcal_value	continuous	Yes: fcal_value $\leq 250 \mu\text{g/g}$	Binary: Yes, no
PROs						
Stool frequency		Stool freq, rect. bleed, NRS	pro_stool_freq	Score (0-3), continuous		Continuous
Rectal bleeding			pro_rect_bleed	Score (0-3), continuous		Continuous
Urgency of defecation			pro_nrs_urgency	Continuous		Continuous
Abdominal pain			pro_nrs_abd_pain	Continuous		Continuous
Quality of sleep			pro_nrs_qual_sleep	Continuous		Continuous
Daily fatigue			pro_nrs_fatigue	Continuous		Continuous

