7.2 Analysis methods

7.2.1 Primary analysis

In the primary analysis, all patients will be analyzed using the FAS set.

Proportions of patients achieving clinical, IBDQ and biochemical response and remission at W8 and W16 will be calculated and reported with the associated 95% Wilson confidence interval.

The course of continuous secondary outcomes (PMS, IBDQ score, PROs and fCAL) and of the exploratory additional PMS subscore outcomes over time will be depicted by box plots showing medians, quartiles, and outlying values. For these outcomes and for Medians and associated quartiles at baseline, W8, and W16 will be reported in a table.

For these outcomes, the change from baseline will be calculated at each time point as the observed value minus the value measured at baseline. The course of change over time, will be depicted by box plots showing medians, quartiles, and outlying values. Medians and associated quartiles at W8 and W16 will be reported in a table.

The course of fCAL over time will be shown separately for patients with and without clinical response as well as for patients with and without remission at W8 and W16. Medians and associated quartiles at W8 and W16 will be reported in a table.

Correlation between PRO outcomes and PMS, PMS subscores, IBDQ score and fCAL concentrations will be assessed at BL, W8 and W16 by the Spearman correlation coefficient. For each time point the correlation coefficient will be presented in a table.

Average daily dose of Tofacitinib during the trial, active UC and others additional outcomes assessed via ultrasound, number of comorbidities and EIM number, improvement, and new occurrence will be described at W8 and 16 in descriptive tables. Categorical variables will be summarized as number and proportion, continuous variables as median with quartiles range or mean with standard deviation, as appropriate.

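### The SAP's coding rule for clinical response, the primary endpoint, has the subtraction reversed: worsening by 2 or more PMS points counts as response, and improvement short of remission does not

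*SAP*

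**What the plan says.** In SAP section 7.1, Table 7-a, the definition column for the primary outcome reads "1) reduction in PMS from baseline of ≥ 2 points or (2) achieving clinical remission". The derivation column of the same row gives the coding rule as "Yes: If (PMS at W8- PMS at baseline ≥ 2", continued by "OR PMS at W8 ≤ 2 AND pms_stool_freq<2 AND pms_rect_bleed<2 AND pms_glob_ass<2 at W8". The Week 16 row has the same definition and the same order of subtraction: "Yes: If (PMS at W16- PMS at baseline ≥ 2".

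Protocol section 8.1.1.1 defines response as "1) reduction in PMS of ≥ 2 points from baseline or (2) achieving clinical remission as described above". It scores PMS from 0 to 9, with higher values for more severe disease. SAP section 4.3 sums the three items, each scored from 0 (normal) to 3 (most severe), and does not reverse them. SAP section 7.2.1 fixes the sign of change: "the change from baseline will be calculated at each time point as the observed value minus the value measured at baseline".

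The footnote to Protocol section 9.5.2 gives a different threshold: "Reduction in PMS from baseline of >2 points or (2) achieving clinical remission".

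**The concern.** The definition and the coding rule in one table row contradict each other. On a scale where higher is worse, Week 8 minus baseline ≥ 2 is a deterioration of at least 2 points. A programmer who works from the derivation column would count deteriorating patients as responders. The same programmer would miss every patient who improved by 2 or more points but stopped short of remission.

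The error would reach:
- the primary endpoint;
- clinical response at Week 16;
- the fCAL summaries split by clinical response, which are part of the objective on fCAL as an early surrogate marker;
- the repeat of these analyses in the on-tofacitinib set, if it is run.

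Clinical remission, and fCAL split by remission, are not affected.

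SAP section 7.8 has a second statistician reproduce the primary analysis. If both programs follow the derivation column, they will agree on the wrong answer.

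**Working it through.** **1. The plan's own figures.** The Wilson interval for p = 0.60 has centre (p + z²/2n)/(1 + z²/n) and half-width z·√(p(1−p)/n + z²/4n²)/(1 + z²/n), with z = 1.96.
- n = 60: 47.4 to 71.4%.
- n = 18: 37.6 to 78.9%.

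Both match SAP section 3.3. No stated figure is in dispute; the fault is in the rule.

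**2. Direction, compared across the rules in Table 7-a.**

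| Outcome | Better is | Coded as | Direction |
|---|---|---|---|
| FMS response | lower | baseline − visit ≥ 3 | correct |
| IBDQ response | higher | visit − baseline ≥ 16 | correct |
| Clinical response, W8 and W16 | lower | visit − baseline ≥ 2 | reversed |

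Under the sign convention of SAP 7.2.1, a reduction of at least 2 would be a change of ≤ −2. Protocol section 9.2 uses the same sign (mean change about −3.1). The table of protocol changes in SAP section 9 lists no change to the primary endpoint definition.

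**3. Examples** (subscores in the order stool frequency, bleeding, global assessment).

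| Baseline | Week 8 | W8 − baseline | By definition | As coded |
|---|---|---|---|---|
| 6 (2,2,2) | 3 (1,1,1) | −3 | response | no |
| 9 (3,3,3) | 2 (2,0,0) | −7 | response | no |
| 6 (2,2,2) | 8 (3,3,2) | +2 | no response | yes |
| 6 (2,2,2) | 2 (1,1,0) | −4 | response | yes, through remission only |

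**4. All score patterns.** Every pair of baseline and Week 8 subscore triples was classified by both rules, for an assumed baseline PMS of at least 4. Of 1166 patterns that improve by 2 or more, 858 are coded as non-response, and the other 308 count only because they meet remission. All 406 patterns that worsen by 2 or more are coded as response. With the assumed baseline floor varied from 3 to 6, the lost share of improving patterns runs from 858/1206 = 71% to 666/806 = 83%. These are counts of possible patterns, not expected shares of patients.

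**5. Effect on the rate.** Coded rate = remission rate + rate of worsening by ≥ 2 without remission. The documents give neither term. Assuming remission of 20–40% and worsening of 0–10%:
- lowest: 20 + 0 = 20% (Wilson, n = 18: 7.7 to 42.9%);
- highest: 40 + 10 = 50% (29.0 to 71.0%).

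**6. Simulated illustration.** Baseline was normal with the protocol's SD of 1.3 and an assumed mean of 6 or 7. Mean change was −2.0 or −2.3, chosen so that correct response is near 60%. Scores were rounded and limited to 0–9, and remission was simplified to PMS ≤ 2. With an SD of change of 2.6, which Protocol 9.2 calls its worst case:

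| Baseline mean, mean change | Correct rule | As coded | Threshold >2 |
|---|---|---|---|
| 6, −2.0 | 58.1% | 38.1% | 44.6% |
| 6, −2.3 | 62.4% | 40.5% | 49.3% |
| 7, −2.0 | 57.6% | 25.4% | 42.8% |
| 7, −2.3 | 62.0% | 27.3% | 47.3% |

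Worsening by ≥ 2 accounts for roughly 5 to 8 percentage points. For 18 patients, 0.60 × 18 ≈ 11 responders would be reported as about 5 to 7 (0.25 × 18 = 4.5; 0.41 × 18 = 7.4).

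**7. Threshold.** PMS is an integer score, so >2 requires a 3-point drop. In the table above this lowers the correct rate by about 13 to 15 percentage points.

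**The case against.** The strongest reply is that the intent is unmistakable. The correct definition stands beside the faulty rule and is repeated in the protocol. The documents contain no program, so nothing shows that the slip was coded. SAP 7.8 does not say that the second statistician works from the derivation column. The planned outputs also print the definition of response and tabulate PMS change, so a reversed result might be noticed. All of this stands, and it makes the finding a specification error rather than a demonstrated error in results. It does not make the rule right, because the derivation column is what a programmer would implement.

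The size depends on chosen inputs. With an SD of change of 1.84 (1.3 × √2, assuming independent visits) and the same mean changes, the coded rate is about 15–32% and worsening about 1.4–2.7%. With the protocol's mean change of −3.1 and SD 2.6, the correct rate is about 73% and the coded rate 34–48%. The figures are therefore illustrations, not bounds. The direction is the same in every case, and the coded rate is well below the correct one.

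The >2 footnote is a weaker point. It occurs once, a sign lost in text extraction cannot be excluded, and the SAP uses a threshold of 2. It would not need urgent correction on its own.

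**Conclusion.** The concern holds. As written, the SAP's rule for the primary endpoint is reversed at both Week 8 and Week 16. It counts as responders the patients who worsen by 2 or more points, and it drops those who improve by 2 or more without reaching remission. Patients who improve into remission are still classified correctly. This conclusion follows from the text alone and needs no assumption.

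The numerical effect does rest on assumptions, because the remission rate, the worsening rate and the baseline mean are not given. A true rate near 60% would plausibly be reported as somewhere between 20 and 50%. With 18 patients, one misclassification shifts the estimate by 1/18 = 5.6 percentage points. Because this is the primary endpoint, it must be corrected before the analysis is relied on. The >2 footnote is a lesser inconsistency to settle at the same time.

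**What to change.** In SAP Table 7-a, replace the two clinical response derivations with:

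- Week 8: Yes if (PMS at baseline − PMS at W8 ≥ 2) OR (PMS at W8 ≤ 2 AND all three subscores at W8 < 2).
- Week 16: the same rule, with W16 in place of W8.

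Check the analysis program and the second statistician's program against the corrected rule. Test cases such as 6 (2,2,2) to 3 (1,1,1), which must be a response, and 6 (2,2,2) to 8 (3,3,2), which must not, are enough to show the sign. If any output was produced under the reversed rule, rerun clinical response at both visits, the fCAL tables and figures split by response, and any on-tofacitinib repeat.

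In the Protocol 9.5.2 footnote, change >2 to ≥2 to match Table 3, section 8.1.1.1 and the SAP, or record the discrepancy in a note to file.

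The cost is one SAP line per visit and a short code check. No new data are needed, the planned precision is unchanged (60% with n = 18 still gives 37.6 to 78.9%), and patients are not affected. A formal protocol amendment for the footnote would carry the usual approval steps, which is a reason to prefer a note to file if no other amendment is planned.

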- A follow-up contact with participant must be scheduled at the end of the AE/SAE active collection period as defined in [Section 8.3.1](#). Safety monitoring will generally continue for an additional 4 weeks (28 days) after Week 16 visit, or after the discontinuation/withdrawal date for participants who discontinue the study prematurely.
- Study-specific discontinuation form will be used to collect reason for study or drug discontinuation, clinical and other undertaken procedures at discontinuation, as well as outcome, where applicable.
- Extent of disease is defined based on endoscopic findings. Endoscopy is not mandatory. Disease extent will only be assessed if endoscopy is performed as part of SOC. Endoscopy is expected at either screening/baseline visit and again at either Week 8 or Week 16 visits.
- Mayo Endoscopic subscore is based on endoscopic findings. Mayo Endoscopic subscore and PMS will be used to calculate FMS. FMS will only be calculated if endoscopy is performed as part of SOC and according to physician's assessment. Endoscopy is expected at either screening/baseline visit and again at either Week 8 or Week 16 visits.
- Data from IUS will be collected and analyzed in an exploratory fashion, only if available and performed as part of SOC.

Other procedures between study visits:

PROs and fCAL levels will be regularly assessed between scheduled study visits. [Table 2](#) summarizes the frequency of these assessments during the study period. Refer to [STUDY ASSESSMENTS AND PROCEDURES](#) section ([Section 8](#)) of the protocol for detailed information on each procedure and assessment required for compliance with the protocol.

Table 2. Schedule of Procedures Between Study Visits

* Stool samples can be collected at +/- 3 days starting from week 2.

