PMS physician's global assessment subscore	Continuous	Variable: pms_glob_ass Derivation: At each reported time point. 4 answers are possible. Answers are converted to score from 0 (normal) to 3 (more severe condition).
Full Mayo score	Continuous	Variables: PMS score (see above), ra_mayo_subscore Derivation: At each reported time point. For each variable, 4 answers are possible for the ra_mayo_subscore variable. Answers are converted to score from 0 (normal) to 3 (severe disease), scores obtained for the PMS score and the ra_mayo_subscore variable are then summed up. If any of the variables used to derive the score is missing the score is coded as missing.
Participant's age	Continuous	Used variables: ic_date, ymob Derivation: Date of signature of the informed consent in mm.yyyy – the date of birth in mm.yy. Result is given in year and rounded to one decimal point
EIM improvement status at week_x (x can be equal to 8 or 16)	Continuous	Variables: eim_cat, eim_subcat_muco, eim_subcat_muscu, eim_subcat_ocular, eim_subcat_hepa, eim_activity Derivation: For each EIM (defined by the variables eim_cat, eim_subcat_muco, eim_subcat_muscu, eim_subcat_ocular, eim_subcat_hepa) -'No worsening' if

CTU Bern	SAP for: Study A3921395 KIC-START	Version: 1.0
----------	-----------------------------------	--------------

CTU Bern	Template: Statistical Analysis Plan (SAP)	Version: 03
	Code: CS_STA_TEM-11	Valid from: 28.02.2019

Variable definition	Variable type	Derivation
		<pre>eim_activity at baseline ='Active at assessment' AND eim_activity at week_x ='Active at assessment' OR eim_activity at baseline ='Past, but not active' AND eim_activity at week_x ='Past, but not active' OR EIM at baseline AND EIM not mentionned at week_x -'Worsened' if eim_activity at baseline ='Past, but not active' AND eim_activity at week_x ='Active at assessment' -'Improved' if eim_activity at baseline ='Active at assessment' AND eim_activity at week_x ='Past, but not active' -'New occurrence' if No EIM at baseline AND eim_activity at week_x ='Active at assessment'</pre>
Number of comorbidities	Continuous	
Used variables:
 
co_morb_yn co_morb
 
Derivation: at bl, W8 and 16.
 
If co_morb_yn== 'yes' count the number of different entries for co_morb If co_morb_yn== 'no' 0

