Weekly fatigue		FACIT-F	"pro_facit_an1", "pro_facit_an12", "pro_facit_an14", " pro_facit_an15",	Continuous	See section 4.3	Continuous

CTU Bern	SAP for: Study A3921395 KIC-START	Version: 1.0
----------	-----------------------------------	--------------

CTU Bern	Template: Statistical Analysis Plan (SAP)	Version: 03
CTU Bern	Code: CS_STA_TEM-11	Valid from: 28.02.2019

u^b^b
UNIVERSITÄT
BERN

Outcome	Definition	eCRF sheet	Variable	Variable type	Derivation	Outcome type
			"pro_facit_an16", "pro_facit_an2", "pro_facit_an3", "pro_facit_an4", "pro_facit_an5", "pro_facit_an7", "pro_facit_an8", "pro_facit_hi12", "pro_facit_hi7".			
IBDQ		PRO IBDQ	pro_ibdq_1 to 32	Continuous	See section 4.3	Continuous
PMS		PMS	PMS score (see section 4.3)	Continuous		Continuous
Clinical response						
fCAL		fCAL	fcal_value	Continuous		Continuous
EXPLORATORY OUTCOMES						
FMS response at W8/W16.	FMS response: decrease from baseline total Mayo score of ≥ 3 points and $\geq 30\%$, with an accompanying decrease in the rectal bleeding subscore of ≥ 1 or absolute rectal bleeding subscore ≤ 1	PMS & SOC Assessment	ra_full_mayo (calculated as described in section 4.3) pms_rect_bleed	Continuous	[(ra_full_mayo at BL - ra_full_mayo at W8 (or 16)) ≥ 3] AND [(ra_full_mayo at BL - ra_full_mayo at W8 (or 16)) / ra_full_mayo at BL ≥ 0.3] AND [pms_rect_bleed at BL - pms_rect_bleed at W8 (or W16) ≥ 1 OR pms_rect_bleed at W8 (or W16) ≤ 1]	Binary: Yes, no

CTU Bern	SAP for: Study A3921395 KIC-START	Version: 1.0
----------	-----------------------------------	--------------

CTU Bern	Template: Statistical Analysis Plan (SAP)	Version: 03
	Code: CS_STA_TEM-11	Valid from: 28.02.2019

u^b^b
UNIVERSITÄT
BERN

Outcome	Definition	eCRF sheet	Variable	Variable type	Derivation	Outcome type
remission at W8/W16	Remission: a total Mayo score of ≤ 2 , with no subscore > 1 and a rectal bleeding subscore of 0	PMS & SOC Assessment	ra_full_mayo (calculated as described in section 4.3) pms_stool_freq pms_glob_ass	continuous	ra_full_mayo at W8/16 ≤ 2 AND [pms_stool_freq ≤ 1 AND pms_glob_ass ≤ 1 at W8/16 AND pms_rect_bleed at W8/16 = 0]	Binary: Yes, no
mucosal healing at W8/W16.	Mucosal healing: a Mayo endoscopic subscore of ≤ 1	SOC Assessment	ra_mayo_subscore	continuous	ra_mayo_subscore at W8/16 ≤ 1	Binary: Yes, no

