response according to IUS assessment at W8/W16.	According to treating physician's assessment of bowel wall thickness, normalization and extension; bowel wall vascularity, loss of stratification, loss of colonic hastration, structure formation and hyperechoic reaction adjacent to the bowel wall.	SOC Assessment	ra_global_eval	categorical	Yes: ra_global_eval %in% c('response', 'remission')	Binary: Yes, no
remission according to IUS assessment at W8/W16.	According to treating physician's assessment of bowel wall thickness, nor-	SOC Assessment	ra_global_eval	categorical	Yes: ra_global_eval = 'remission'	Binary: Yes, no

CTU Bern	SAP for: Study A3921395 KIC-START	Version: 1.0
----------	-----------------------------------	--------------

CTU Bern	Template: Statistical Analysis Plan (SAP)	Version: 03
Code: CS_STA_TEM-11	Valid from: 28.02.2019	Page 28 of 44

u^b^b
UNIVERSITÄT
BERN

Outcome	Definition	eCRF sheet	Variable	Variable type	Derivation	Outcome type
	malization and extension; bowel wall vascularity, loss of stratification, loss of colonic haustration, structure formation and hyperecho- genic reaction adjacent to the bowel wall.					
individual improvement in EIM reported at BL at W8/W16 15 outcome/variables	EIM improvement for EIM reported at BL	Extra Intestinal Manifestations (EIM)	eim_cat eim_subcat eim_activity ('Past, but not active' vs. active at assessment)	-Categorical -Categorical - Binary	See section 4.3 for EIM improvement status at week_x (x can be equal to 8 or 16) Yes: EIM improvement status == Improved	Binary: Yes, no
Categorical improvement 5 variables/outcomes	EIM improvement is reported for at least one of the subcategories of the studied category.	Extra Intestinal Manifestations (EIM)	eim_cat eim_activity ('Past, but not active' vs. active at assessment)	-Categorical - Binary	Yes: eim_cat==the studied category AND eim_activity=='Past, but not active'	Binary: Yes, no
ADDITIONAL EXPLORATORY OUTCOMES						
Average daily dose of Tofacitinib during the trial		Baseline Tofacitinib Change in Tofacitinib Exposure			See section 4.3	Binary: <15mg tofa-citinib/day,

CTU Bern	SAP for: Study A3921395 KIC-START	Version: 1.0
----------	-----------------------------------	--------------

CTU Bern	Template: Statistical Analysis Plan (SAP)	Version: 03
	Code: CS_STA_TEM-11	Valid from: 28.02.2019

u^b^b
UNIVERSITÄT
BERN

Outcome	Definition	eCRF sheet	Variable	Variable type	Derivation	Outcome type
	Tofacitinib discontinuation					≥15 mg tofacitinib/day

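### Three SAP derivations for exploratory or descriptive outputs do not match their own definitions or labels: full-Mayo remission, EIM category improvement and baseline dose class

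*SAP*

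**What the plan says.** **Full-Mayo remission (SAP 7.1, Table 7-a, exploratory).** The definition cell reads "Remission: a total Mayo score of ≤ 2 , with no subscore > 1 and a rectal bleeding subscore of 0". The derivation cell in the same row reads "ra_full_mayo at W8/16 ≤ 2 AND [pms_stool_freq ≤ 1 AND pms_glob_ass ≤ 1 at W8/16 AND pms_rect_bleed at W8/16 = 0". SAP 4.3 builds the full Mayo score by adding the endoscopic subscore (`ra_mayo_subscore`, 0 to 3) to the partial Mayo score.

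**EIM category improvement (same table, exploratory).** The definition is "EIM improvement is reported for at least one of the subcategories of the studied category". The derivation is "Yes: eim_cat==the studied category AND eim_activity=='Past, but not active". The row above it, for individual manifestations, uses "Yes: EIM improvement status == Improved". SAP 4.3 gives the status 'Improved' to "eim_activity at baseline ='Active at assessment' AND eim_activity at week_x ='Past, but not active" and the status 'No worsening' to, among others, "eim_activity at baseline ='Past, but not active' AND eim_activity at week_x ='Past, but not active".

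**Baseline predominant tofacitinib dose (SAP 4.3; reported in Table 6-a).** The variable has two levels, below 15 mg/day and 15 mg/day or more. The derivation codes it yes/no. It is 'yes' if the recorded level is 10 mg twice daily, or if the level is Other with a daily dose under 15 mg, and 'no' otherwise.

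SAP section 9 lists none of these as an intended change from the protocol.

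**The concern.** The derivation cells are close to executable code, and the SAP does not say which cell prevails when definition and derivation disagree. A programmer who follows the derivations would misclassify some participants in two rows of the efficacy table (SAP 8.2.2) and in one row of the baseline table.

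The first two errors run one way. A remission rule without the endoscopic limit can only admit extra participants. A category rule without a baseline condition can only enlarge the numerator.

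The denominators will be small. Only 18 participants were enrolled, and endoscopy is standard of care only. The schedule footnote says "Endoscopy is expected at either screening/baseline visit and again at either Week 8 or Week 16 visits", so having all 18 evaluable at one visit would require everyone to be examined at that visit. One misclassified participant would be visible in the reported percentage.

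**Working it through.** **Check of the interval formula.** Wilson limits are [p + z²/(2n) ± z·√(p(1−p)/n + z²/(4n²))] / (1 + z²/n), with z = 1.96. For p = 0.60 and n = 18 this gives 37.62% to 78.86%, which reproduces the 37.6 to 78.9% in SAP 3.3. That figure is not an input to this point; it only confirms the formula used below.

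**(a) Remission.** Four subscores (stool, bleeding, global assessment, endoscopy), each 0 to 3, give 4⁴ = 256 patterns.

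- *Definition:* bleeding is 0 and the other three are each 0 or 1 with sum ≤ 2. That is 2³ − 1 = 7 patterns.
- *Derivation:* bleeding is 0, stool and global assessment are each 0 or 1, total ≤ 2, endoscopy otherwise free. If stool + global = 0 (1 way), endoscopy may be 0, 1 or 2, giving 3. If the sum is 1 (2 ways), endoscopy may be 0 or 1, giving 4. If the sum is 2 (1 way), endoscopy must be 0, giving 1. Total: 3 + 4 + 1 = 8 patterns.
- *Difference:* one pattern, endoscopy 2 with all other subscores 0. Adding endoscopy ≤ 1 returns exactly the 7 defined patterns.

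The extra participant would be reported as in remission but not as having mucosal healing, because the next row does require an endoscopic subscore ≤ 1.

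The shift per misclassified participant is 100/N percentage points. N is not in the documents, so these values are assumed: 5.6 (N = 18), 11.1 (N = 9), 16.7 (N = 6). With 18 participants split evenly over the two visits (N = 9), 2/9 = 22.2% (Wilson 6.3 to 54.7) would become 3/9 = 33.3% (12.1 to 64.6).

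**(b) EIM category.** For one manifestation there are nine baseline-by-visit states. The category rule, applied at the visit, is met by three:

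| Baseline | Visit | Status in SAP 4.3 | Category rule |
|---|---|---|---|
| Active | Past | Improved | Yes |
| Past | Past | No worsening | Yes |
| Not reported | Past | none assigned | Yes |

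Past manifestations are a recorded baseline level in Table 6-a, so past-to-past is foreseeable.

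With k subcategories there are 9ᵏ patterns. For k = 1 to 5, which covers every category in Table 7-b, no pattern with an 'Improved' manifestation fails the category rule. The numerator can therefore only grow. For k = 2 (musculoskeletal), out of 81:

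- category Yes: 81 − 6² = 45
- at least one 'Improved': 81 − 8² = 17
- Yes without any 'Improved': 45 − 17 = 28
- of those 28, the other manifestation was active at baseline in 2 × 2 × 2 = 8

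The last line shows that limiting N to participants with an active manifestation would not remove the error. If the odd not-reported-to-past state is dropped, 64 patterns remain, the excess is 7² − 6² = 13, and 4 of those include a manifestation active at baseline. These are counts of logical patterns, not expected rates. One extra participant adds 5.6 points at an assumed N of 18 and 33.3 points at an assumed N of 3.

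**(c) Baseline dose.** 10 mg × 2 = 20 mg/day.

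| Recorded | mg/day | Rule | Class by the labels |
|---|---|---|---|
| 10 mg twice daily | 20 | yes | ≥ 15 |
| Other | under 15 | yes | < 15 |
| Other | 15 or more | no | ≥ 15 |

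'Yes' contains both classes and 'no' contains part of the upper one, so no assignment of yes/no to the two labels works.

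**The case against.** The strongest reply concerns weight. The study is descriptive with no hypothesis testing (SAP 3.4), two of the outputs are exploratory, and the third is a single baseline row that feeds nothing else because section 9 drops the subgroup and baseline-effect analyses. For (a) and (b) the intended rule stands beside the wrong one, so intent is not in doubt. The discordant remission pattern is a single one: it needs a standard-of-care endoscopy at that visit and a normal global rating despite moderate endoscopic disease. The not-reported-to-past state enlarges the 28 of 81. The dose rule may be a one-character slip: with ≥ in place of <, 'yes' would be the upper class. If every participant started on 10 mg twice daily, nobody would be mixed. The evaluable N values are assumed. The individual EIM row is restricted to manifestations reported at baseline, so only the category row lacks a denominator.

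Most of this stands as a limit on importance, and the point about the denominator is accepted. None of it removes the contradictions. A correct definition does not repair a wrong derivation. Quality control (SAP 7.8) covers reproduction of the primary analysis. Section 7.2.1, under that heading, mentions EIM improvement but not clearly full-Mayo remission, and two statisticians coding the same wrong rule would agree with each other.

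**Conclusion.** The concern holds on all three parts. Followed literally, the remission rule admits one pattern that the definition excludes (8 against 7). The EIM category rule counts manifestations that were never active at baseline. The dose rule fits neither of its labels. The errors in (a) and in the numerator of (b) can only favour a better result; (c) makes one baseline row impossible to label correctly.

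Whether any participant shows the affected patterns cannot be known from the documents. The percentage-point shifts rest on assumed denominators. These three errors do not affect the primary endpoint. The weight is low, but the SAP should be corrected.

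**What to change.** - **Remission:** add `ra_mayo_subscore` ≤ 1 at the same visit to the derivation.
- **EIM category improvement:** derive it as at least one manifestation in the category with the section 4.3 status 'Improved' at that visit (Week 8 or Week 16), and state the denominator for the category row of the table in 8.2.2.
- **Baseline dose:** reconcile the rule with its labels by converting each recorded dose to total mg/day and classifying on that number. This concerns variable coding only and takes no view on dosing.
- **Presentation, separate from the three:** average daily dose is binary in SAP 4.3 and Table 7-a but shown as median or mean in the 8.4 table shell; align them.

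The cost is three derivation rows, one stated denominator and one variable-type entry. No new data are needed, and the corrections restore definitions and labels the SAP already contains.
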